### 6.2.3 End of trial and follow-up

#### Termination of trial medication – End of trial

The following will be obtained and / or performed:

- physical examination including vital signs, body weight and ECOG performance score
- adverse events
- laboratory examinations: urine dipstick

The conclusion of patient participation should be completed for all patients together with their last visit. The conclusion of patient participation will be completed during the final visit (day 22) for patients treated per protocol. For patients, who were withdrawn or dropped out of the trial, the end of trial investigations should be completed at the last visit.

Imaging and tumour assessment need to be done only if not yet performed within the past three weeks.

#### Follow up visit

All patients who completed a treatment course (all visits performed including visit at day 22) and are not eligible for a further course will be followed up until progression, lost to follow up or treatment with another anti-cancer drug. The intervals for follow up are every six weeks for the first 3 months and then every three months, respectively. At each follow up visit adverse events will be reported in case they were not recovered at the end of treatment of the last course. Performance of physical examination and ECG as well as determination of safety lab parameters is optional. The ECOG performance score will be reported. No tumour assessment is requested if the patient has progressive disease and/or received another anti-cancer therapy. CT or MRI examinations will be handled according to the RECIST guideline.

### 6.2.4. Missed visits

If a visit is missed and the patient reports to the investigator between this visit and the next one, the missed visit should be done with the actual date and the reason should be given for the delayed visit. The next visit, however, should take place at the scheduled time after administration of the trial drug.

## 6.3 REMOVAL OF PATIENTS FROM THERAPY ASSESSMENT

A patient has to be withdrawn from the trial if:

- the patient withdraws consent

- the patient is no longer able to participate in the trial (e.g. adverse events, surgery, concomitant diagnoses, concomitant therapies or administrative reasons); in such case the Investigator's reason for a patient removal must be recorded in the appropriate page of the eCRF.
- eligibility criteria are violated

All withdrawals will be documented and the reason for withdrawal recorded and discussed, as necessary, in the final report of the trial.

The patients are free to discontinue their participation in this study at any time. The investigator may also stop patient's participation, if the patient is no longer able to attend study visits e.g. due to worsening of disease. A patient can be withdrawn after discussion between the sponsor and the investigator if eligibility criteria are violated or the patient fails to comply with the protocol (e.g. non-compliance to study visits, see 6.3.1).

### **6.3.1 Replacement of patients**

Patients withdrawn or patients who miss more than one visit during their first treatment course will be replaced. Patients who miss one visit may be replaced after discussion between the sponsor and the investigator.

Patients who withdraw due to DLT will not be replaced.

## 7. STATISTICAL METHODS AND DETERMINATION OF SAMPLE SIZE

### 7.1 STATISTICAL DESIGN / MODEL

This phase I trial will be performed to determine the safety, tolerability, MTD, pharmacokinetics and preliminary therapeutic effects of BI 6727 (cf. 2.2. and 2.3. for definition of endpoints) in patients with various advanced and/or metastatic solid tumours for whom no established antitumour treatment options are available.

The dose escalation procedure is described in 4.1.3. Cohorts of patients will be entered sequentially into escalating dosage tiers with the aim to identify the maximum tolerated dose of BI 6727.

This study is open-label, which allows the safety of each dosage of BI 6727 to be assessed before treating additional patients with higher doses. Patients will not be randomized; they will be assigned to the cohort that is being filled at the time the patient is ready to enter the trial.

#### 7.1.1. Safety and tolerability evaluation

Safety and tolerability of BI 6727 will be assessed in terms of changes in laboratory parameters, vital signs, the incidence and severity and causality of adverse events and of toxicities according to CTCAE criteria version 3.0. The results will be reported for each dose level separately as well as in terms of overall means, if appropriate.

The results will be displayed for the first course and overall courses separately.

#### 7.1.2. Pharmacokinetic evaluation

If feasible, the following PK parameters will be calculated:

$C_{\max}$  (maximum concentration of the analyte in plasma)

$t_{\max}$  (time from dosing to maximum concentration)

$AUC_{0-\infty}$  (area under the concentration-time curve of the analyte in plasma over the time interval from 0 extrapolated to infinity)

$AUC_{0-tz}$  (area under the concentration-time curve of the analyte in plasma over the time interval from 0 to the last quantifiable time point  $t_z$ )

% $AUC_{0-tz}$  (the percentage of the  $AUC_{0-\infty}$  that is obtained by extrapolation)

$\lambda_z$  (terminal rate constant in plasma),  $t_{1/2}$  (terminal half-life of the analyte in plasma)

MRT (mean residence time of the analyte in the body after intravenous administration)

CL (total clearance of the analyte in the plasma after intravascular administration)

$V_z$  (apparent volume of distribution during the terminal phase  $\lambda_z$  following an intravascular dose)

$V_{ss}$  (apparent volume of distribution at steady state following intravascular administration)

$Ae_{0-24/48}$  (amount of analyte that is eliminated in urine from the time point 0 to time point 24 and 48 h respectively)

$fe_{0-24/48}$  (fraction of analyte eliminated in urine from time point 0 to time point 24 and 48 h respectively)

$CL_{R,0-24/48}$  (renal clearance of the analyte from the time point 0 to time point 24 and 48 h respectively)

The pharmacokinetic parameters  $C_{max}$ ,  $AUC_{0-\infty}$  and  $AUC_{0-tz}$  will be descriptively explored concerning dose proportionality.

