## 10. APPENDICES

### 10.1 HANDLING OF PLASMA AND URINE DATA AND DERIVATION OF PHARMACOKINETICS PARAMETERS

Analyte plasma concentrations will be plotted graphically versus time for all subjects as listed in the analyte plasma concentration-time tables. For the presentation of the mean profiles, the arithmetic/geometric mean and the planned blood sampling times will be used.

Concentrations will be used for calculations in the format that is reported in the bioanalytical report. The data format for descriptive statistics of concentrations will be identical with the data format of the respective concentrations. For the calculation of pharmacokinetic parameters, only concentrations within the validated concentration range will be used. The descriptive statistics of pharmacokinetic parameters will be calculated using the individual values with the number of decimal places as provided by the evaluation program. Then the individual values as well as the descriptive statistics will be reported with three significant digits in the clinical trial report. The actual sampling times will be used. For predose samples, the actual sampling time will be set to zero.

Concentration data identified with NOS (no sample available), NOR (no valid result), NOA (not analyzed), BLQ (below the limit of quantification), and NOP (no peak detectable) will be ignored and not replaced by zero at any time point (applies also to the lag phase including the pre-dose value). Descriptive statistics of concentrations at specific time points will be calculated only when at least 2/3 of the individuals have concentrations within the validated concentration range. The overall sample size to decide whether the “2/3 rule” is fulfilled will be based on the total number of samples intended to be drawn for that time point (i.e., BLQ, NOR, NOS, NOA, NOP are included).

Non-compartmental pharmacokinetic parameters will be determined using WinNonlin or another validated program.

In the non-compartmental analysis, concentration data identified with NOS, NOR, and NOA will not be considered. BLQ and NOP values in the lag phase will be set to zero. The lag phase is defined as the period between time zero and the first time point with a concentration above the quantification limit. All other BLQ and/or NOP values of the profile will be ignored.

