where  $C'_{tz}$  is the concentration predicted by the regression line for the time  $t_z$  (time of last measurable concentration of the analyte in plasma). The area under the concentration-time curve over the time interval from 0 to the last quantifiable plasma concentration ( $AUC_{0-tz}$ ) will be calculated by the linear up/log down method as described above.

**%AUCtz-∞:** The percentage of the  $AUC_{0-\infty}$  will be obtained by extrapolation according to the following equation:

$$\% AUC_{tz-\infty} = \frac{AUC_{0-\infty} - AUC_{0-tz}}{AUC_{0-\infty}} \times 100$$

**MRT:** The mean residence time after intravenous bolus injection will be calculated as follows:

$$MRT = \frac{AUMC_{0-\infty}}{AUC_{0-\infty}}$$

In order to compare the mean residence time after intravenous bolus administration (MRT) and intravenous infusion (MRTinf), the following equation will be used in addition, where T represents the infusion time.

$$MRT = MRT_{inf} - (T \times 0.5)$$

The area under the first moment curve from time 0 to infinity (AUMC0-∞) is calculated according to:

$$AUMC_{0-\infty} = AUMC_{0-tz} + \frac{C'_{tz} \times tz}{\lambda_z} + \frac{C'_{tz}}{\lambda_z^2}$$

**CL:** The total clearance after intravenous administration will be determined according to the following equation:

$$CL = \frac{\text{Dose}}{AUC_{0-\infty}}$$

(F = absolute bioavailability factor)

**Vz:** The apparent volume of distribution during the terminal phase after intravascular administration will be determined according to the following equation:

$$V_z = \frac{CL}{\lambda_z}$$

**Vss:** After single intravenous bolus administration or intravenous infusion when the mean residence time has been adapted as described above, the distribution volume in the steady state will be calculated according:

$$V_{ss} = CL_{ss} \times MRT_{ss}$$

**fet1-t2:** The fraction excreted is calculated according to

$$fe_{t1-t2} = \frac{Ae_{t1-t2}}{\text{Dose}} \times 100$$

where **Aet1-t2** is the total quantity of the analyte that is excreted in urine over the time interval t1 to t2. This may represent the product of urine volume and urine analyte concentration for one time interval, as well as the cumulative amounts excreted calculated as the sum of the excreted amounts of subsequent time intervals.

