**CLR,t1-t2:** The renal clearance (CLR) will be calculated as the quotient of the quantity of the analyte that is excreted in urine from the time point t1 until the time point t2 (Aet1-t2) and the area under the concentration-time curve within the same time interval (AUCt1-t2).

$$CL_{R,t1-t2} = \frac{Ae_{t1-t2}}{AUC_{t1-t2}}$$

**gMean, gCV:** The geometric mean (gMean) and coefficient of variation, gCV (given in %), will be calculated by the formulae:

$$gMean = \exp \left[ \frac{1}{n} \sum_{i=1}^n \ln(x_i) \right] = \exp \left[ \ln(\bar{x}) \right]$$

$$gCV(\%) = 100 \cdot \sqrt{\exp [Var(\ln(x_i))] - 1}$$

where

$$Var(\ln(x_i)) = \frac{1}{n-1} \sum_{i=1}^n \left[ \ln(x_i) - \bar{\ln(x_i)} \right]^2.$$

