3.2 STATISTICAL DESIGN / MODEL

This phase I trial was performed according to an uncontrolled, open label, accelerated dose titration design to determine the MTD of BI 6727 in patients with advanced solid tumours.

The design is that of a 3+3 fixed dose escalation design ([R01-0028](#)) using a toxicity guided approach.

Patients with advanced solid tumours were eligible for this trial. BI 6727 was given as a short infusion over 60 minutes on day 1 of each three week treatment course during the escalation phase. The additional patients treated at the phase II recommended dose of 300 mg to investigate QTc changes, were assigned to one of two infusion time schedules: BI 6727-1h-infusion in course 1 and BI 6727-2h-infusion in course 2 or BI 6727-2h-infusion in course 1 and BI 6727-1h-infusion in course 2. The infusion schedule in courses 3 and higher was always the one hour infusion time.

Patients were not randomized, instead they were selected by the investigators and assigned to the cohort being filled at the time the patient was ready to enter the trial. Thus, the analyses will focus on the exploratory description of the results of each cohort, rather than comparing cohorts.

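### AUC0-tz is one of the dose-proportionality measures, but its end time can move with dose through the assay limit, so a dose-proportional drug can look supra-proportional on it

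*Protocol*

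**What the plan says.** Protocol section 7.1.2 lists the pharmacokinetic parameters and says that three of them, Cmax, AUC0-inf and AUC0-tz, "will be descriptively explored concerning dose proportionality". It defines AUC0-tz as the "area under the concentration-time curve of the analyte in plasma over the time interval from 0 to the last quantifiable time point". Appendix 10.1 restates tz as the "time of last measurable concentration of the analyte in plasma".

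Appendix 10.1 ties tz to the assay. For parameter calculation "only concentrations within the validated concentration range will be used". Values below quantification in the lag phase are set to zero, and after that "All other BLQ and/or NOP values of the profile will be ignored". No end time common to all doses is given for the dose-proportionality comparison.

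The dose range is wide. Protocol section 4.1.3.1 starts at 12 mg, and SAP section 3.2 refers to "The additional patients treated at the phase II recommended dose of 300 mg to investigate QTc changes". The range is therefore at least 300 / 12 = 25-fold; the highest dose tested is not stated in the available text.

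**The concern.** Under linear kinetics every concentration scales with dose, but the assay limit does not. A 12 mg profile reaches the limit no later than a 300 mg profile. If it reaches it earlier, its AUC0-tz leaves out a late part of the curve that the 300 mg AUC0-tz includes, and the comparison then mixes dose with length of integration. Late samples are sparse (24, 48, 96, 168 and 336 h), so losing one sample can halve the window.

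The pharmacokinetic profile is a secondary objective (protocol section 2.1), and section 7.3.2 also plans to compare AUC with safety and efficacy endpoints. What is at stake is an accurate description of how exposure rises with dose. Appendix 10.1 adds one aggravating rule: where the terminal rate constant cannot be determined, only parameters that do not need it are reported. AUC0-tz could then be the only one of the two AUC measures left, most likely in the low tiers where it is most truncated.

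**Working it through.** The documents state no slope, acceptance limit, assay limit or half-life, so there is no figure of the plan to reproduce. The check asks what AUC0-tz shows when the drug is exactly dose-proportional.

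**Inputs from the documents.** 60-minute infusion; course 1 samples at 0:15, 0:30, 0:45, 1:00, 1:30, 2, 4, 8, 24, 48, 96, 168 and 336 h; linear up/log down AUC; terminal rate constant from at least three points (last three used here); doses 12 and 300 mg.

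**Assumptions.** Two-phase decline, distribution half-life 1 h, terminal half-life 24, 48, 72 or 120 h, ratio of the terminal to the distribution coefficient (B/A) 0.02, 0.05 or 0.2, and assay limit 0.1, 0.3, 1 or 3% of the 12 mg end-of-infusion concentration. That is 4 × 3 × 4 = 48 scenarios.

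**Formula.** Let e be the share of total AUC lying after tz. Under linear kinetics the dose-normalised ratio is

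R = (1 − e300) / (1 − e12).

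Since tz at 12 mg is never later than at 300 mg, e12 ≥ e300 and R ≥ 1. The systematic error is zero or supra-proportional.

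**One scenario by hand** (half-life 120 h, B/A 0.05, limit 1%; A = 1):
- β = ln 2 / 120 = 0.005776 per h. Total AUC = 1/0.6931 + 0.05/0.005776 = 1.443 + 8.656 = 10.099.
- End of infusion: 0.5/0.6931 + 8.656 × (1 − e^(−β)) = 0.7213 + 0.0499 = 0.7712.
- At 168 h: 0.0499 × e^(−167β) = 0.0190, which is 2.5% of 0.7712 and quantifiable at 12 mg.
- At 336 h: 0.0499 × e^(−335β) = 0.0072, which is 0.93% and below the limit at 12 mg. At 300 mg it is 25 times higher and quantifiable.
- So tz is 168 h at 12 mg and 336 h at 300 mg. e12 = (0.0190/β)/10.099 = 0.326; e300 = (0.0072/β)/10.099 = 0.123.
- R = 0.877 / 0.674 = 1.30.

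**All 48 scenarios**, with the protocol's trapezoidal rule (truth 1.00 throughout):

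| Assay limit, % of 12 mg end-of-infusion concentration | AUC0-tz ratio 300:12 mg | Largest AUC0-inf ratio | AUC0-inf within 2% of truth |
|---|---|---|---|
| 0.1 | 1.00–1.06 | 1.00 | 12 of 12 |
| 0.3 | 1.00–1.15 | 1.02 | 12 of 12 |
| 1 | 1.00–1.30 | 1.14 | 10 of 12 |
| 3, 24 h quantifiable at 12 mg | 1.00–1.90 | 1.20 | 5 of 8 |
| 3, 24 h not quantifiable at 12 mg | 1.56–2.77 | 2.98 | 0 of 4 |

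AUC0-inf is within 2% of truth in 12 + 12 + 10 + 5 + 0 = 39 of 48. AUC0-24 gives 1.00 wherever the 24 h sample is quantifiable at 12 mg.

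**Other kinetic shapes.** A one-phase decline with half-life 110 h gives 1.00 at every limit tried (0.05 to 10%). One-phase with 12 to 48 h gives 1.00 to 1.09 for limits up to 5%. Three-phase with half-lives 0.3, 6 and 110 h gives 1.00 at 0.5% or below, 1.22 at 1%, 1.52 at 2%, 2.59 at 5% and 4.13 at 10%. The size therefore runs from nothing to large, depending on facts the documents do not give.

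**The case against.** The strongest reply is that the plan already holds the remedy. AUC0-inf stands beside AUC0-tz in the same sentence of section 7.1.2, and it is close to the truth in most scenarios. The extrapolated percentage is calculated, and Appendix 10.1 lists the start and end times of the terminal fit. In all nine scenarios where AUC0-inf was off by more than 2%, the fitted 12 mg half-life was shorter than the 300 mg one (for example 7 against 24 h, or 1.6 against 120 h), so an alert reader would have a clue. This largely stands, and it limits the weight of the point.

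It does not dispose of it. AUC0-inf fails where truncation is worst, because the terminal phase is not seen at the low dose. The extrapolated percentage has no limit or action attached and need not give warning: in a two-phase case with half-lives 1 and 72 h and a limit at 10%, it was 15% at 12 mg and 16% at 300 mg while the AUC0-inf ratio was 3.97.

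Two further objections stand as limits. All analyses are descriptive (section 7.2), so no error rate is involved. And SAP section 7.5 refers the pharmacokinetic analysis to a reference document whose name is redacted, which may already specify a common interval.

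A reader might also infer that dose escalation or the MTD is at risk, or that an artefact would be reported as saturating clearance. The documents do not support either. Escalation is toxicity-guided (protocol sections 3.2 and 4.1.3.1), no dose decision uses AUC0-tz, and Appendix 10.1 computes clearance from AUC0-inf.

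**Conclusion.** The point holds as a conditional. If low tiers fall below the assay limit before 336 h, AUC0-tz can make a dose-proportional drug look supra-proportional; if every tier is quantifiable to 336 h, there is no bias. Whether low tiers do drop out early cannot be told from the documents, so it would be wrong to say that the planned comparison is biased.

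The size rests on the assumed kinetics and assay limit. The figure 2.77 should not be taken as typical: it is one corner of the grid (B/A 0.02, half-life 120 h, limit 3%), where the 12 mg profile ends at 8 h and AUC0-24 could not be observed either. Where 24 h is quantifiable at 12 mg, the largest ratio in the two-phase grid is 1.90.

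The consequence is a possible misdescription of a secondary pharmacokinetic result. This is a cheap improvement, not a flaw in the primary analysis.

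**What to change.** In protocol section 7.1.2, for dose proportionality only, replace AUC0-tz by an AUC over an interval common to all tiers: AUC0-24 and AUC0-48, or, where a tier is not quantifiable that far, the longest interval quantifiable in every tier. Fix the rule for choosing the interval before dose-normalised values are inspected. Keep Cmax and AUC0-inf, read AUC0-inf together with its extrapolated percentage and the time limits of the terminal fit, and keep AUC0-tz as a listed parameter.

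The cost is about one sentence. AUC0-24 and AUC0-48 are already needed, because Appendix 10.1 divides the amount excreted in urine by "the area under the concentration-time curve within the same time interval" to obtain renal clearance over 0–24 and 0–48 h. No samples or patients are added.

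The drawback is coverage. In the two-phase grid AUC0-24 holds 17 to 86% of total AUC, and only 17 to 40% at a half-life of 120 h, so alone it could miss non-linear terminal elimination. AUC0-inf must therefore stay beside it.

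If the redacted reference document already sets a common interval, citing it in section 7.1.2 is enough. A power-model slope of log parameter on log dose would be a reasonable summary, but is optional.

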### 7.1.3. Therapeutic efficacy evaluation

Tumour response will be the parameter for therapeutic efficacy. Tumour response will be evaluated according to the RECIST guidelines (see ISF). Tumour response will be assessed by the amount of patients with complete response (CR), partial response (PR), stable disease (SD) or progressive disease (PD), respectively. The number of patients with objective response (i.e. CR or PR) will be provided per dose level.

## 7.2 NULL AND ALTERNATIVE HYPOTHESES

All analyses in this trial are descriptive and exploratory by nature. Any statistical tests are performed only to provide a statistical framework from which to view the results and providing aid for planning further studies. No formal statistical inferences are foreseen.

## 7.3 PLANNED ANALYSES

Only one analysis population (the treated set) will be considered for efficacy and safety analyses. No Per protocol population will be used for analyses, however protocol violations will be described.

**Treated Set** consists of all patients who received at least one application of BI 6727

### 7.3.1 Primary analyses

Non evaluable patients will be replaced. The total number of study patients depends on the toxicity encountered. Patients who are evaluable for toxicity but not for efficacy need not be replaced.

The primary endpoint for this study is the tolerability and safety of BI 6727 as reflected by the Maximum Tolerated Dose (MTD) of BI 6727

Determination of MTD will be done using data from patients receiving the first course of BI 6727. Depending on the drug related toxicity observed in this study, up to six patients will be treated in each dose cohort. To increase the safety database at the presumed Phase II dose, a total of 24 patients will be enrolled at MTD.

MTD will be defined as the dose of BI 6727 that is one dose cohort below that dose at which two or more out of a maximum of six patients experienced DLT. At the maximum tolerated dose, no more than one patient out of six patients may experience Dose Limiting Toxicity (DLT, for definition, see section 5.2.1).

MTD will be defined on the basis of DLT observed during the first course. However, for those patients who receive a further infusion, unusual or unexpected toxicities will be considered for the purposes of confirming the MTD

To assess safety of BI 6727, all DLT's occurring during the first or repeated treatment courses will be reported as significant adverse events.

